## **D. Research Design and Methods**

We will use a prospective double-blind randomized placebo-controlled study design. Subjects will be enrolled as inpatients or during the initial office visit by orthopaedic clinical research staff. After routine evaluation reveals that a patient meets the inclusion and exclusion criteria (below), informed consent will be obtained. Demographic data will be recorded. Patients will be block randomized by opaque, sealed-envelope to either a treatment group or a placebo group (N=20; N=10 treatment, N=10 placebo).

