### ***Covariates***

#### ***Demographics***

- Age
- Race/ethnicity
- Gender
- BMI

- Co-morbidities
- Fracture classification
- Time until definitive fixation
- Tobacco use
- Workers compensation status
- Level of education
- Marital status
- Personal income
- Health insurance
- Working status before injury

These data will be abstracted from the medical record by the research staff.

*Additional Outcomes*

- Time until full weight bearing
- Time until return to work
- Compliance with weight bearing status
- Compliance with prescribed treatment

These data will be patient reported

*Complications*

- Nonunion
- Malunion
- Infection: Deep
- Infection: Superficial
- Osteomyelitis
- Wound breakdown
- Skin slough: partial thickness
- Skin slough: full thickness
- Additional surgeries: Strayer recession, Achilles lengthening, hardware removal, amputation, or arthrodesis.
- Rehospitalizations

These data will be captured during clinical exam at each office visit

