### **D.3 Methods**

Orthopaedic surgery attendings and residents will identify potential study candidates during the initial consultation based on the presence of a tibial plafond fracture. If the patient meets the inclusion and exclusion criteria (noted above), a member of the treatment team will discuss the study with eligible patients. If the patient expresses interest in the study, the physician will notify the research staff. Orthopaedic Clinical Research staff will describe study procedures in detail and go through the informed consent process to enroll the patient in the study. Patients will be informed of the “off-label” usage of botulinum toxin injections as well as the potential side effects.

Once informed consent is obtained and the patient is enrolled in the study, the attending surgeon will classify the fracture based on the AO/OTA classification system (Figure 1). Study participants will then be block randomized and assigned by sequentially numbered sealed opaque envelopes to one of the two treatment groups based on computerized selection: those who receive intramuscular botulinum toxin injections at the time of definitive fixation, and those who receive placebo. Patients with bilateral pilon fractures and no other lower extremity injuries of the tibia, ankle, or foot that would further impair dorsiflexion stretching or other

rehabilitation exercises will have each extremity randomized and evaluated separately. Patients with a unilateral tibial plafond fracture and no injury of the contralateral tibia, ankle, or foot will be placed in a subgroup of patients who will have their unaffected extremity examined for comparison. Patients with an injury to the contralateral extremity that would exclude them from this subset will have only the extremity with the pilon fracture analyzed.

[figure not shown]

Figure 1.

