The results of the patients receiving Botox will be compared to those who received placebo. Average dorsiflexion will be determined and compared between the two groups as well as the percentage of patients who achieve 10 degrees or more of dorsiflexion. If applicable, the average dorsiflexion in the injured extremity will also be compared to the uninjured extremity to determine the average difference in dorsiflexion between the two groups. For statistical analysis, differences with a p value of <0.05 will be considered statistically significant.

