#### **D.4 Data Management**

All data will be entered into REDCap, a web-based data entry and management system that provides logic checks on input and checks for invalid entries. Data will be entered continuously as they are collected and stored in univariate form. We will also run standard checks for outliers, duplicates and other types of errors which may occur within a complex data file. All data files will be password protected and hard copies of blinded patient records will be maintained in locked cabinets in the research office.

*Data Analysis:* In order to determine that the randomization process produced comparable groups, we will use t-tests and cross-tabulations to compare patients in the treatment group to patients in the placebo group on the following variables: age, race, gender, BMI comorbidities, fracture classification, time until definitive fixation, tobacco use, workers compensation status, level of education, marital status, personal income, health insurance, working status before surgery, compliance with weight-bearing restrictions, compliance with prescribed treatment, time until full weight bearing and return to work.

Analyses will follow the intent-to-treat paradigm, under which all patients will be analyzed according to the treatment group to which they were randomized. Intention to treat analyses of outcomes will be conducted in two stages. First, we will conduct a bivariate analysis to examine relationships between assigned treatment

group, primary and secondary outcomes, and potential covariates and confounders (demographics, injury characteristics, co-morbidities). We will then use the results to build a multivariate model to predict primary and secondary outcomes based on treatment type.

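### Fracture class is recorded before allocation but neither balanced by the randomisation nor fixed in the model, which costs precision and interpretability with 20 patients

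*Combined protocol and SAP*

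**What the plan says.** Section D sets the size and the method: "Patients will be block randomized by opaque, sealed-envelope to either a treatment group or a placebo group (N=20; N=10 treatment, N=10 placebo". D.3 Methods gives the order of events. After consent, "the attending surgeon will classify the fracture based on the AO/OTA classification system"; the next sentence continues, "Study participants will then be block randomized and assigned by sequentially numbered sealed opaque envelopes to one of the two treatment groups". Neither section names a stratification factor or a block size.

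The covariate list in D.2 includes "Fracture classification". D.4 examines outcomes against "potential covariates and confounders (demographics, injury characteristics, co-morbidities". It handles imbalance afterwards, in two ways:

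- A comparability check that covers fracture classification: "In order to determine that the randomization process produced comparable groups, we will use t-tests and cross-tabulations".
- A model whose covariates are not fixed in advance: "We will then use the results to build a multivariate model to predict primary and secondary outcomes based on treatment type".

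The only threshold given, at the end of D.3, is that "differences with a p value of <0.05 will be considered statistically significant".

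**The concern.** Blocking fixes the number of patients per arm. It does nothing for the mix of fracture types within each arm, and with 10 per arm that mix can differ noticeably by chance. The protocol gives reason to think the mix matters. Section B links articular comminution and bone loss to poor results, and B.3 presents lost motion as a consequence of severe joint-surface injury. Dorsiflexion is measured only at 6 and 12 months, so there is no baseline value to adjust for, and injury severity is one of the few baseline predictors available.

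The pilot result will also be used. Under D.5, clearly inferior results in the Botox arm would mean that the full trial is not run. D.5 and D.8 use the data for the power analysis and foresee pooling with the full cohort. D.8 makes pooling conditional on an unchanged protocol, so introducing stratification after the pilot would count against pooling.

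**Working it through.** **Inputs from the documents.** 20 patients, 10 per arm (Section D); class known before allocation (D.3); threshold 0.05 (end of D.3). The plan states no imbalance probability or power figure, so there is none to reproduce.

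**Assumptions.** Share of type C: 50% or 75%. Effect of type C on dorsiflexion, δ: 3, 5 or 8 degrees. Within-class SD: 7 degrees. None of these is in the documents.

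**1. Chance imbalance.** With K type C fractures among 20 and 10 patients drawn to one arm, the number X of type C in that arm is hypergeometric(20, K, 10).

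- K = 10: P(7:3 or worse) = 0.179. Exactly 7:3 (either way) accounts for 2 × 0.0779 = 0.156, and 8:2 or worse for 0.023.
- K = 15: P(9:6 or worse) = 0.303. Exactly 9:6 accounts for 2 × 0.1355 = 0.271, and 10:5 for 0.033.

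Small unstratified blocks do not help. In simulation with each patient type C at probability 0.5, the arms differ by 3 or more type C patients in about 26% of runs, for blocks of 2 or 4. With stratification in such blocks, a difference of 3 or more cannot occur.

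**2. Would the balance check notice?** For a 7:3 split, Fisher's exact p = 0.18 and uncorrected chi-square p = 0.07. For 9:6, the values are 0.30 and 0.12. Neither reaches 0.05. The rarer splits do (8:2 has Fisher p = 0.023; 10:5 has 0.033).

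**3. Would the model pick class up?** D.4 gives no selection rule. If it were p < 0.05 in the bivariate step, with 10 patients in each class and SD 7, the chance of selecting a real class effect of 3, 5 or 8 degrees is about 15%, 33% or 68%.

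**4. Shift in the unadjusted arm difference.** Shift = (difference in type C share) × δ.

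- 7:3 split: 0.4 × δ = 1.2, 2.0 or 3.2 degrees.
- 9:6 split: 0.3 × δ = 0.9, 1.5 or 2.4 degrees.

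**5. Precision.** With type C probability q, the unadjusted variance of the arm difference is 0.2 × (49 + δ²q(1 − q)), where 0.2 = 1/10 + 1/10 and 49 = 7². Stratified and adjusted, the ideal is 0.2 × 49 = 9.80. With incomplete blocks simulated, it is about 9.85 to 9.94.

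| δ (degrees) | Unadjusted, q = 0.5 | Reduction | Unadjusted, q = 0.75 | Reduction |
|---|---|---|---|---|
| 0 | 9.80 | −1.4% to −0.5% | 9.80 | −1.4% to −0.5% |
| 3 | 10.25 | 3.0% to 3.9% | 10.14 | 2.0% to 2.8% |
| 5 | 11.05 | 10.0% to 10.9% | 10.74 | 7.4% to 8.3% |
| 8 | 13.00 | 23.5% to 24.2% | 12.20 | 18.5% to 19.3% |

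For δ = 5 and q = 0.5 the SE falls from √11.05 = 3.32 to about √9.85 = 3.14 degrees.

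**6. Cost in arm size.** Relative variance is (1/n₁ + 1/n₂)/0.2. For 11:9 it is 1.010, and for 12:8 it is 1.042. In simulation, blocks of 2 gave at worst 11:9 (about 25% of runs). Blocks of 4 gave at worst 12:8, with unequal arms in about 37%.

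**The case against.** The strongest reply is that nothing is broken. Allocation is computer-generated and concealed, chance imbalance is already reflected in the standard error, and the study is a pilot acknowledged to lack power. D.4 checks balance on fracture class and provides for a model. The exclusions (Gustilo-Anderson IIIB and IIIC, nerve, vascular, tendon and foot injuries) already narrow severity. D.2 lists many covariates without ranking them, and D.4 calls these characteristics only potential confounders. No dorsiflexion result is given by fracture class; B.3 reports whole-cohort means of 7 to 10 degrees. The envelopes deliver only part of the gain: with 10 of 20 type C, adjusting without stratifying gives a variance of about 10.43 (SE 3.23), so stratifying takes off only about a further 0.1 degree of SE.

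Most of this stands, and it limits the point to precision and interpretability. Two parts do not remove it. The check passes the likely imbalances and the model is likely to omit class, so the D.4 safeguards are weak at this size. Nor do unequal arms cancel the gain, because the 9.85 to 9.94 above already includes them. At δ = 3, adjusting without stratifying (10.43) is worse than not adjusting (10.25), so the two changes belong together.

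A reader might infer that the randomisation is biased, or that a 2-degree shift rivals the treatment effect sought. The documents support neither. Unstratified allocation is unbiased on average, and no target effect is stated. The illustrative shift of 2.0 degrees is also smaller than the SE of about 3.1.

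**Conclusion.** The point holds as a loss of precision and interpretability that is inexpensive to avoid; it is not a fault of validity. The imbalance probabilities depend only on the 10:10 allocation and the assumed number of type C fractures. The shifts and variance reductions depend also on the assumed class effect, and the reductions on SD 7 and the type C share. The gain is roughly 4%, 11% or 24% of variance at a 50% share, and about 2-3%, 8% or 19% at 75%. If class has no effect on dorsiflexion there is no gain and a loss of about 1%. The change is worth making before enrolment, given the intended reuse of the pilot data, but the trial does not depend on it.

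**What to change.** In Section D and D.3, replace the single description of blocked envelopes with two sequentially numbered series, one for AO/OTA 43-B and one for 43-C. Use small permuted blocks in each (for example, of 2 and 4, with the size concealed from enrolling staff), and draw the next envelope from the series matching the class already recorded. D.3 names the classification system but no grouping, so the two-level cut is a proposal to check against Figure 1. Where both limbs of a patient are randomised, the series follows the class of each limb.

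In D.4, state that this two-level factor is included in the dorsiflexion comparison regardless of the bivariate results.

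The cost is a second envelope list, a few lines of text and one degree of freedom. Arm totals may come out at 11:9 (about 1% loss of precision) or, where blocks of 4 are used, at worst 12:8 (about 4%).

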**Table 1: Botox Dosing by Weight**

45-55 kg:	140 U
55-65 kg:	170 U
65-75 kg:	200 U
75-85 kg:	230 U
85-95 kg:	260 U
95-105 kg:	290 U
105-115 kg:	300 U

At the completion of surgery, the gastrocsoleus complex will be injected in four locations (superior medial, superior lateral, inferior medial, and inferior lateral) prior to the application of short leg splint, per the recommendation of prior studies. At each injection site,  $\frac{1}{4}$  of the total dose of botulinum toxin A or normal saline will administered in approximately 0.5 ml injections. The use of EMG or other imaging modalities has been recommended to ensure accuracy of botulinum toxin injection at the target muscle motor end plates, however it is not necessary when injecting the gastrocsoleus complex, even in small children due to its large size and superficial location. The injection sites are illustrated in the figure 2 below:

[figure not shown]

Figure 2

Following definitive fixation and study injections, patients will be placed in a well-padded splint in at least neutral dorsiflexion for two weeks to allow for wound healing. Following wound healing, patients will transition to a removable orthosis and begin range of motion exercises and stretching techniques. All patients will undergo a structured exercise regimen. Each patient will receive a pamphlet at an 8th grade reading level containing a standardized exercise protocol which clearly states the exercises to be utilized, the frequency, and duration. As long as there are no adverse events, patients will proceed to touch down weight bearing at roughly 6 weeks postoperatively and continue their exercise program. Patients will then advance to partial weight bearing at approximately eight weeks and full weight bearing as tolerated at 10 to 12 weeks, as long as no adverse events occur precluding this progression.

Study participants will return to regularly scheduled follow-up appointments to monitor their progress. At each follow-up appointment (2 weeks, 6 weeks, 12 weeks, 6 months, and 1 year), patients will be monitored for signs and symptoms of Botox toxicity. All patients will be seen in follow-up at one of two clinic locations. At each site, research staff familiar with the study will be present along with a device for measuring dorsiflexion in a standardized fashion.

Clinical assessment will be accomplished by physical exam and questionnaires for subjective complaints described above with a member of the Orthopaedic Clinical Research staff. Patients will be asked to complete SF-36, BPI, and FAAM questionnaires at their 6 month and 12 month follow-up visits. Time to full weight bearing, time to return to work, compliance with weight bearing status, and compliance with rehabilitation protocol will all be noted at 6 and 12 months.

At the end of the 6 and 12-month follow-up appointments, ankle dorsiflexion will be assessed using a device to measure dorsiflexion and radiographs in a standardized manner.

Routine radiographs taken as part of standard of care will be used to assess the quality of fracture alignment, range of motion and to follow for boney union or malunion. Radiographic data will be reviewed by a group of three independent observers blinded to the patient and the treatment group. Malunion will be assessed by drawing a line along the subchondral bone of the tibial plafond and a line drawn through the center of the tibial shaft. Deviation of >5 degrees from 90 in either the AP or lateral plane will be considered varus, valgus, or sagittal plane malunion. Clinical union will be defined as the patient's ability to bear full weight on the injured extremity with evidence of boney bridging in at least 2 of 4 cortices. The determination of nonunion will be determined by the attending surgeon's assessment based on radiographic and clinical findings consistent with nonunion, such as hardware failure, failure of boney bridging, and persistent pain at the fracture site beyond what would be expected in a healed fracture.

Study volunteers will be provided with a \$70 patient incentive for their time in completing the health assessment questionnaires and dorsiflexion measurements at 6 months. An additional \$100 will be provided to those who return at 1 year for examination and health assessment questionnaires.

The results of the patients receiving Botox will be compared to those who received placebo. Average dorsiflexion will be determined and compared between the two groups as well as the percentage of patients who achieve 10 degrees or more of dorsiflexion. If applicable, the average dorsiflexion in the injured extremity will also be compared to the uninjured extremity to determine the average difference in dorsiflexion between the two groups. For statistical analysis, differences with a p value of <0.05 will be considered statistically significant.

#### **D.4 Data Management**

All data will be entered into REDCap, a web-based data entry and management system that provides logic checks on input and checks for invalid entries. Data will be entered continuously as they are collected and stored in univariate form. We will also run standard checks for outliers, duplicates and other types of errors which may occur within a complex data file. All data files will be password protected and hard copies of blinded patient records will be maintained in locked cabinets in the research office.

*Data Analysis:* In order to determine that the randomization process produced comparable groups, we will use t-tests and cross-tabulations to compare patients in the treatment group to patients in the placebo group on the following variables: age, race, gender, BMI comorbidities, fracture classification, time until definitive fixation, tobacco use, workers compensation status, level of education, marital status, personal income, health insurance, working status before surgery, compliance with weight-bearing restrictions, compliance with prescribed treatment, time until full weight bearing and return to work.

Analyses will follow the intent-to-treat paradigm, under which all patients will be analyzed according to the treatment group to which they were randomized. Intention to treat analyses of outcomes will be conducted in two stages. First, we will conduct a bivariate analysis to examine relationships between assigned treatment

group, primary and secondary outcomes, and potential covariates and confounders (demographics, injury characteristics, co-morbidities). We will then use the results to build a multivariate model to predict primary and secondary outcomes based on treatment type.

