**B.2 Current Difficulties in Treating Pilon Fractures:** Despite widespread usage of a staged protocol for this injury, good to excellent results are still difficult to attain. Recent studies consistently report “relatively poor physical and psychosocial outcomes” with persistent and severe sequelae. Pollack and colleagues noted that at 3-year follow-up, patients presented with significantly poorer health related outcome scores than age and gender-matched norms. Large proportions of patients with this type of injury present with significant stiffness, swelling, pain, and difficulties with retaining employment, showing that there is still work to be done to improve the outcomes of this devastating injury.

**B.3 Loss of Dorsiflexion:** Limited range of motion is a common and potentially debilitating result of these often severe articular injuries. A minimum of 10 degrees of dorsiflexion is required for normal gait mechanics and loss of this dorsiflexion is termed equinus contracture. Equinus contracture can result in functional limitations as well as be a contributing factor to seemingly unrelated lower limb pathologies including strains, plantar fasciitis, hallux valgus, stress fractures, adult-acquired flat foot, plantar fasciitis, Achilles tendonitis, Charcot arthropathy, diabetic foot ulceration, and metatarsalgia. Gait analysis studies examining limited dorsiflexion in the ankle joint has shown that patients with less than 10 degrees of dorsiflexion begin to experience abnormal stresses at multiple other lower extremity joints. In addition to contributing to these other pathologies, loss of dorsiflexion and pain are the only two independent variables shown to significantly limit functionality in patients recovering from ankle fractures.

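### Time to full weight bearing and return to work appear only in a randomization check by t-tests and cross-tabulations, with no rule for patients who never reach the event; the risk of a misleading comparison is mainly for return to work

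*Combined protocol and SAP*

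**What the plan says.** The Data Analysis paragraph in section D.4 opens with a purpose: "In order to determine that the randomization process produced comparable groups". For that purpose, "we will use t-tests and cross-tabulations to compare patients in the treatment group to patients in the placebo group on the following variables". Most of the list is baseline characteristics, but it closes with "working status before surgery, compliance with weight-bearing restrictions, compliance with prescribed treatment, time until full weight bearing and return to work".

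Section D.2 files the two times elsewhere. "Time until return to work" and time to full weight bearing stand under Additional Outcomes, as patient-reported items. Section D.3 has them noted at the 6- and 12-month visits.

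The two-stage outcome analysis in D.4 names primary and secondary outcomes only. The comparison paragraph at the end of D.3 names only dorsiflexion measures. No censoring rule, survival method or value for patients who do not reach the event appears anywhere, and nothing deals with patients who had no job to return to.

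The baseline work variable is worded in two ways: "working status before surgery" in D.4 and "Working status before injury" in D.2.

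**The concern.** The protocol itself foresees patients who will not reach these events. D.3 makes progress to full weight bearing conditional on the absence of adverse events that rule it out. D.2 lists nonunion, amputation and arthrodesis among the complications. B.2 reports that large proportions of these patients have "difficulties with retaining employment". Others will be lost before 12 months, and a patient not working before injury cannot return to work.

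A t-test needs a number for every patient it includes. With no rule for non-attainers, it can compare only those who succeeded, and who succeeds may depend on the arm. If the toxin adds successes and the added ones come late, they raise the treated mean and the better arm looks slower.

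There is also a fault of role. Both times arise after randomization, so they cannot show whether it produced comparable groups. A treatment effect on them would be read as chance imbalance.

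**Working it through.** **Inputs from the documents.** 10 patients per arm (section D); follow-up to 12 months (D.3); significance at p < 0.05 (D.3; two-sided assumed). The plan gives no power, attainment rate or time distribution for these variables, so there is no figure of its own to reproduce. All rates and times below are assumptions.

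**Step 1: direction, by arithmetic.** The t-test compares means among returners. The mean time not returned, restricted to 12 months, counts everyone: p × (returners' mean) + (1 − p) × 12.

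| Assumed case | Placebo returners' mean | Toxin returners' mean | Placebo restricted mean | Toxin restricted mean |
|---|---|---|---|---|
| 40% v 80% return, equal means | 6 | 6 | 0.4×6 + 0.6×12 = 9.6 | 0.8×6 + 0.2×12 = 7.2 |
| 40% v 80% return, extra 40% average 8 months | 6 | (0.4×6 + 0.4×8)/0.8 = 7 | 9.6 | 0.8×7 + 0.2×12 = 8.0 |

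In the first case the returners' means show no difference, while the toxin arm is 2.4 months better overall. In the second they show toxin 1 month worse, while it is 1.6 months better.

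**Step 2: power in those cases.** Simulation with 10 per arm, normal times (SD 2 months) among returners, 4,000 runs, non-returners censored at 12 months for the log-rank test:
- Equal means: t-test power about 5%, log-rank about 43%.
- Treated mean 7 months: average t-test difference about 1.0 month against toxin, wrong sign in about 79% of estimable runs, significant for harm in roughly 10%.
- In about 4-5% of runs the t-test cannot be computed, because an arm has fewer than two returners.

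**Step 3: a case with attenuation but no reversal.** Exponential times, 50% placebo return by 12 months (rate λ = ln 2/12), hazard ratio 2.
- Returners' mean, 1/λ − 12e^(−12λ)/(1 − e^(−12λ)): placebo 17.31 − 12 = 5.31; toxin 8.66 − 4 = 4.66; difference 0.66 month from unrounded values.
- Restricted mean, (1 − e^(−12λ))/λ: placebo 8.66; toxin 6.49; difference 2.16 months from unrounded values.

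The t-test points the right way but sees about 30% of the difference (0.66/2.16).

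**Step 4: range.**
- Proportional hazards, 40-70% placebo attainment, hazard ratio 2-3, 10 per arm: log-rank power 20-60%, t-test on attainers 3-24%.
- Extra 20-30 percentage points of late attainers (months 8-12) added to 50-70%: log-rank finds the benefit in 8-15% of runs and the t-test in 0.3-0.4%. The t-test is significant for harm in 10-16% of runs at 10 per arm and 52-83% at 50 per arm. A larger sample does not remove the bias.

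**Step 5: full weight bearing.** D.3 plans it at 10 to 12 weeks, so most patients may attain it within a year. At 90% v 95% attainment with equal times, both tests reject at close to the 5% error rate and barely differ. If 80-90% attain it on placebo and toxin adds 10-15 points of late attainers, significant false harm occurs in 3-5% of runs, although the estimate has the wrong sign in 81-91%.

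**The case against.** D.4 does not assign a test to each variable. Return to work could be cross-tabulated as returned or not, which counts non-returners and avoids the selection bias. With 40% v 80% and 10 per arm, an uncorrected chi-square has about 43% power (Fisher's exact test about 25%), close to the log-rank figure. This stands: the 5% v 43% contrast applies only if the t-test is the tool used. But D.2 defines the variable as a time, a cross-tabulation ignores timing, and the plan gives no cut-point for one.

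The sentence is also a comparability table, not a declared efficacy analysis, and these are additional outcomes of a 20-patient pilot that section A says will likely lack power even for its main aims. That limits the stakes. It does not rescue the comparison, because no other is given.

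A reader might infer that the plan commits to t-tests on attainers and expressly drops the rest, or that apparent harm here would end the programme under the clause in D.5 on clearly inferior results. The documents support neither. Dropping non-attainers follows from what a t-test requires, not from a stated rule, and D.5 does not tie its clause to these variables.

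The before-surgery wording is a slip, not evidence that the wrong variable is collected, since D.2 defines it correctly.

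**Conclusion.** The concern holds in this form: two post-randomization outcomes sit in a randomization check, their only named analysis is a mixed phrase, and under its natural reading for a time that analysis uses a group selected after treatment. It can miss a real gain or show it as harm. Reversal requires that the added attainers be late; under proportional hazards the result is attenuation. Every size rests on assumed rates and times. The risk is mainly for return to work and is small for full weight bearing if nearly all attain it.

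It would be too strong to say that the trial's main conclusions are at risk, because no aim or hypothesis uses these times. The practical cost is a misleading estimate in data that D.5 and D.8 intend for planning a full trial and possibly pooling with it. The change is worth making but is not critical.

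**What to change.** In D.4, take both times out of the randomization check and analyse them as outcomes by randomized arm:
- Kaplan-Meier curves, a log-rank test and the difference in restricted mean time to 12 months, with patients who have not reached the event censored at last contact, 12 months at most.
- The proportion attained by 6 and by 12 months.
- Return to work limited to patients working before injury, using the D.2 variable. Align the D.4 wording with it: D.7 puts definitive fixation about 14 days after injury, so status before surgery may differ.

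This takes a few sentences and no new data. The cost is a smaller return-to-work sample and less power than the 43% shown: at an assumed 7 per arm, about 32% in the same scenario. The times are patient reported and noted only at 6 and 12 months, so they remain approximate under any method, and the report should say so.
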